### **17.5. Case Report Form Completion**

Case report forms are prepared and provided by the sponsor for each subject in electronic format. All data relating to the study must be recorded in the eCRF. All eCRF entries, corrections, and alterations must be made by the investigator or authorized study-site personnel. The investigator must verify that all data entries in the eCRF are accurate and correct.

The study data will be transcribed by study-site personnel from the source documents onto an eCRF, if applicable. Study-specific data will be transmitted in a secure manner to the sponsor.

Worksheets may be used for the capture of some data to facilitate completion of the eCRF. Any such worksheets will become part of the subject's source documents. Data must be entered into eCRF in English. The eCRF must be completed as soon as possible after a subject visit and the forms should be available for review at the next scheduled monitoring visit.

All subjective measurements (eg, pain scale information or other questionnaires) will be completed by the same individual who made the initial baseline determinations whenever possible.

If necessary, queries will be generated in the electronic data capture (eDC) tool. If corrections to an eCRF are needed after the initial entry into the eCRF, this can be done in either of the following ways:

- Investigator and study-site personnel can make corrections in the eDC tool at their own initiative or as a response to an auto query (generated by the eDC tool).
- Sponsor or sponsor delegate can generate a query for resolution by the investigator and study-site personnel.

### **17.6. Data Quality Assurance/Quality Control**

Steps to be taken to ensure the accuracy and reliability of data include the selection of qualified investigators and appropriate study sites, review of protocol procedures with the investigator and study-site personnel before the study, periodic monitoring visits by the sponsor, and direct transmission of clinical laboratory data from a central laboratory into the sponsor's database. Written instructions will be provided for collection, handling, storage, and shipment of samples.

Guidelines for eCRF completion will be provided and reviewed with study-site personnel before the start of the study. The sponsor will review eCRF for accuracy and completeness during on-site monitoring visits and after transmission to the sponsor; any discrepancies will be resolved with the investigator or designee, as appropriate. After upload of the data into the study database they will be verified for accuracy and consistency with the data sources.

## **17.7. Record Retention**

In compliance with the ICH/GCP guidelines, the investigator/institution will maintain all eCRF and all source documents that support the data collected from each subject, as well as all study documents as specified in ICH/GCP Section 8, Essential Documents for the Conduct of a Clinical Trial, and all study documents as specified by the applicable regulatory requirement(s). The investigator/institution will take measures to prevent accidental or premature destruction of these documents.

Essential documents must be retained until at least 2 years after the last approval of a marketing application in an ICH region and until there are no pending or contemplated marketing applications in an ICH region or until at least 2 years have elapsed since the formal discontinuation of clinical development of the investigational product. These documents will be retained for a longer period if required by the applicable regulatory requirements or by an agreement with the sponsor. It is the responsibility of the sponsor to inform the investigator/institution as to when these documents no longer need to be retained.

If the responsible investigator retires, relocates, or for other reasons withdraws from the responsibility of keeping the study records, custody must be transferred to a person who will accept the responsibility. The sponsor must be notified in writing of the name and address of the new custodian. Under no circumstance shall the investigator relocate or dispose of any study documents before having obtained written approval from the sponsor.

If it becomes necessary for the sponsor or the appropriate regulatory authority to review any documentation relating to this study, the investigator/institution must permit access to such reports.

## **17.8. Monitoring**

The sponsor will use a combination of monitoring techniques as specified in the monitoring guidelines to monitor this study.

The sponsor will perform on-site monitoring visits as frequently as necessary. The monitor will record dates of the visits in a study site visit log that will be kept at the study site. The first post-initiation visit will be made as soon as possible after enrollment has begun. At these visits, the monitor will compare data entered into the eCRF with the source documents (eg, hospital/clinic/physician's office medical records). The nature and location of all source documents will be identified to ensure that all sources of original data required to complete the eCRF are known to the sponsor and study-site personnel and are accessible for verification by the sponsor study-site contact. If electronic records are maintained at the study site, the method of verification must be discussed with the study-site personnel.

Direct access to source documents (medical records) must be allowed for the purpose of verifying that the recorded data are consistent with the original source data. Findings from this review will be discussed with the study-site personnel. The sponsor expects that, during monitoring visits, the relevant study-site personnel will be available, the source documents will

be accessible, and a suitable environment will be provided for review of study-related documents. The monitor will meet with the investigator on a regular basis during the study to provide feedback on the study conduct.

In addition to on-site monitoring visits, remote contacts can occur. It is expected that during these remote contacts, study-site personnel will be available to provide an update on the progress of the study at the site.

## **17.9. Study Completion/Termination**

### **17.9.1. Study Completion/End of Study**

The study is considered completed with the last visit for the last subject participating in the study. The final data from the study site will be sent to the sponsor (or designee) after completion of the final subject visit at that study site, in the time frame specified in the Clinical Trial Agreement.

### **17.9.2. Study Termination**

The sponsor reserves the right to close the study site or terminate the study at any time for any reason at the sole discretion of the sponsor. Study sites will be closed upon study completion. A study site is considered closed when all required documents and study supplies have been collected and a study-site closure visit has been performed.

The investigator may initiate study-site closure at any time, provided there is reasonable cause and sufficient notice is given in advance of the intended termination.

Reasons for the early closure of a study site by the sponsor or investigator may include but are not limited to:

- Failure of the investigator to comply with the protocol, the requirements of the IEC/IRB or local health authorities, the sponsor's procedures, or GCP guidelines
- Inadequate recruitment of subjects by the investigator
- Discontinuation of further development of JNJ-56136379

## **17.10. On-Site Audits**

Representatives of the sponsor's clinical quality assurance department may visit the study site at any time during or after completion of the study to conduct an audit of the study in compliance with regulatory guidelines and company policy. These audits will require access to all study records, including source documents, for inspection. Subject privacy must, however, be respected. The investigator and study-site personnel are responsible for being present and available for consultation during routinely scheduled study-site audit visits conducted by the sponsor or its designees.

Similar auditing procedures may also be conducted by agents of any regulatory body, either as part of a national GCP compliance program or to review the results of this study in support of a

regulatory submission. The investigator should immediately notify the sponsor if he or she has been contacted by a regulatory agency concerning an upcoming inspection.

### **17.11. Use of Information and Publication**

All information, including but not limited to information regarding JNJ-56136379 or the sponsor's operations (eg, patent application, formulas, manufacturing processes, basic scientific data, prior clinical data, formulation information) supplied by the sponsor to the investigator and not previously published, and any data, including pharmacogenomic or exploratory biomarker research data, generated as a result of this study, are considered confidential and remain the sole property of the sponsor. The investigator agrees to maintain this information in confidence and use this information only to accomplish this study, and will not use it for other purposes without the sponsor's prior written consent.

The investigator understands that the information developed in the study will be used by the sponsor in connection with the continued development of JNJ-56136379, and thus may be disclosed as required to other clinical investigators or regulatory agencies. To permit the information derived from the clinical studies to be used, the investigator is obligated to provide the sponsor with all data obtained in the study.

The results of the study will be reported in a Clinical Study Report generated by the sponsor and will contain data from all study sites that participated in the study as per protocol. Recruitment performance or specific expertise related to the nature and the key assessment parameters of the study will be used to determine a coordinating investigator for the study. Results of pharmacogenomic or exploratory biomarker analyses performed after the Clinical Study Report has been issued will be reported in a separate report and will not require a revision of the Clinical Study Report. Study subject identifiers will not be used in publication of results. Any work created in connection with performance of the study and contained in the data that can benefit from copyright protection (except any publication by the investigator as provided for below) shall be the property of the sponsor as author and owner of copyright in such work.

Consistent with Good Publication Practices and International Committee of Medical Journal Editors guidelines, the sponsor shall have the right to publish such primary (multicenter) data and information without approval from the investigator. The investigator has the right to publish study site-specific data after the primary data are published. If an investigator wishes to publish information from the study, a copy of the manuscript must be provided to the sponsor for review at least 60 days before submission for publication or presentation. Expedited reviews will be arranged for abstracts, poster presentations, or other materials. If requested by the sponsor in writing, the investigator will withhold such publication for up to an additional 60 days to allow for filing of a patent application. In the event that issues arise regarding scientific integrity or regulatory compliance, the sponsor will review these issues with the investigator. The sponsor will not mandate modifications to scientific content and does not have the right to suppress information. For multicenter study designs and substudy approaches, secondary results generally should not be published before the primary endpoints of a study have been published. Similarly, investigators will recognize the integrity of a multicenter study by not submitting for publication

data derived from the individual study site until the combined results from the completed study have been submitted for publication, within 18 months after study end date, or the sponsor confirms there will be no multicenter study publication. Authorship of publications resulting from this study will be based on the guidelines on authorship, such as those described in the ICMJE Recommendations for the Conduct, Reporting, Editing and Publication of Scholarly Work in Medical Journals, which state that the named authors must have made a significant contribution to the conception or design of the work; or the acquisition, analysis, or interpretation of the data for the work; and drafted the work or revised it critically for important intellectual content; and given final approval of the version to be published; and agreed to be accountable for all aspects of the work in ensuring that questions related to the accuracy or integrity of any part of the work are appropriately investigated and resolved.

### **Registration of Clinical Studies and Disclosure of Results**

The sponsor will register and disclose the existence of and the results of clinical studies as required by law.

## ATTACHMENTS

### Attachment 1: Contraceptive and Barrier Guidance

#### Definitions

##### **Woman of Childbearing Potential (WOCBP)**

A woman is considered fertile following menarche and until becoming postmenopausal unless permanently sterile (see below).

##### **Woman Not of Childbearing Potential**

- **premenarchal**

A premenarchal state is one in which menarche has not yet occurred.

- **postmenopausal**

A postmenopausal state is defined as no menses for 12 months without an alternative medical cause. A high FSH level ( $>40$  IU/L or mIU/mL) in the postmenopausal range may be used to confirm a postmenopausal state in women not using hormonal contraception or HRT, however in the absence of 12 months of amenorrhea, a single FSH measurement is insufficient. If there is a question about menopausal status in women on HRT, the woman will be required to use one of the non-estrogen-containing hormonal highly effective contraceptive methods if she wishes to continue HRT during the study.

- **permanently sterile**

Permanent sterilization methods include hysterectomy, bilateral salpingectomy, bilateral tubal occlusion/ligation procedures, and bilateral oophorectomy.

Note: If the childbearing potential changes after start of the study (eg, a premenarchal woman experiences menarche) or the risk of pregnancy changes (eg, a woman who is not heterosexually active becomes active), a woman must begin a highly effective method of contraception, as described throughout the inclusion criteria.

If reproductive status is questionable, additional evaluation should be considered.

#### Examples of Contraceptives

EXAMPLES OF CONTRACEPTIVESa,b ALLOWED DURING THE STUDY INCLUDE:	
USER INDEPENDENT	
Highly Effective Methods That Are User Independent Failure rate of <math>\leq 1\%</math> per year when used consistently and correctly.	

 
• Implantable progestogen-only hormone contraception associated with inhibition of ovulationc
 
• Intrauterine device (IUD)
 
• Intrauterine hormone-releasing system (IUS)
 
• Bilateral tubal occlusion
 
• Vasectomized partner (Vasectomized partner is a highly effective contraceptive method provided that the partner is the sole sexual partner of the woman of childbearing potential and the absence of sperm has been confirmed. If not, additional highly effective method of contraception should be used. Spermatogenesis cycle is approximately 74 days.)
 
	

USER DEPENDENT
Highly Effective Methods That Are User Dependent Failure rate of <1% per year when used consistently and correctly.

 
Combined (estrogen- and progestogen-containing) hormonal contraception associated with inhibition of ovulationb 
 
oral
 
intravaginal
 
transdermal
 
injectables
 
 
 
Progestogen-only hormone contraception associated with inhibition of ovulationc 
 
oral
 
injectable
 
 
 
Sexual abstinence (Sexual abstinence is considered a highly effective method only if defined as refraining from heterosexual intercourse during the entire period of risk associated with the study intervention. The reliability of sexual abstinence needs to be evaluated in relation to the duration of the study and the preferred and usual lifestyle of the subject.)
 

NOT ALLOWED AS SOLE METHOD OF CONTRACEPTION DURING THE STUDY (not considered to be highly effective - failure rate of >1% per year)

 
Progestogen-only oral hormonal contraception where inhibition of ovulation is not the primary mode of action.
 
Male or female condom with or without spermicided
 
Cap, diaphragm, or sponge with spermicide
 
A combination of male condom with either cap, diaphragm, or sponge with spermicide (double-barrier methods)d
 
Periodic abstinence (calendar, symptothermal, post-ovulation methods)
 
Withdrawal (coitus-interruptus)
 
Spermicides alone
 
Lactational amenorrhea method (LAM)
 

 
Contraceptive (birth control) use by men or women should be consistent with local regulations regarding the acceptable methods of contraception for those participating in clinical studies.
 
Typical use failure rates may differ from those when used consistently and correctly. Use should be consistent with local regulations regarding the use of contraceptive methods for subjects participating in clinical studies.
 
Hormonal contraception may be susceptible to interaction with JNJ-56136379, which may reduce the efficacy of the contraceptive method. In addition, consider if the hormonal contraception may interact with JNJ-56136379.
 
Male condom and female condom should not be used together (due to risk of failure with friction).
 

**Attachment 2: Cardiovascular Safety - Abnormalities****ECG**

All important abnormalities from the ECG readings will be listed.

Abnormality Code	ECG parameter			
	HR	PR	QRS	QT corrected
Abnormalities on actual values				
Abnormally low	< 45 bpm	NAP	-	-
Abnormally high	≥ 120 bpm	> 220 ms	≥ 120 ms	-
Borderline prolonged QT	-	-	-	450 ms < QTc ≤ 480 ms
Prolonged QT	-	-	-	480 ms < QTc ≤ 500 ms
Pathologically prolonged QT	-	-	-	QTc > 500 ms
Abnormalities on changes from baseline (ΔQTc)				
Normal QTc change	-	-	-	ΔQTc < 30 ms
Borderline QTc change	-	-	-	30 ms ≤ ΔQTc ≤ 60 ms
Abnormally high QTc change	-	-	-	ΔQTc > 60 ms

NAP = not applicable

For absolute QTc parameters the categories are defined based on the ICH E14 Guidancea

**Vital Signsb**

The following abnormalities will be defined for vital signs:

Abnormality Code	Vital Signs parameter		
	Pulse	DBP	SBP
Abnormalities on actual values			
Abnormally low	≤ 45 bpm	≤ 50 mmHg	≤ 90 mmHg
Grade 1 or mild	-	> 90 mmHg - < 100 mmHg	> 140 mmHg - < 160 mmHg
Grade 2 or moderate	-	≥ 100 mmHg - < 110 mmHg	≥ 160 mmHg - < 180 mmHg
Grade 3 or severe	-	≥ 110 mmHg	≥ 180 mmHg
Abnormally high	≥ 120 bpm	-	-

a The clinical evaluation of QT/QTc interval prolongation and proarrhythmic potential for non-antiarrhythmic drugs CHMP/ICH/2/04, May 2005.

b The classification of AEs related to hypotension and hypertension will be done according to the DAIDS grading scale.

**Attachment 3: Rash Management**

For subjects reporting rash, the following should be done.

**Subjects should be informed that they should contact their doctor immediately when they notice any skin reaction. The skin reaction should be evaluated in the clinic the same day (if possible) or the next day.**

All rash events should be captured in the AE section of the eCRF. A separate Rash page will be completed in case of a rash event.

Grading of rash events will be based on the DAIDS Toxicity Grading Scale.

Monitoring of the evolution of rash events will be performed as described in [Table 8](#).

**Table 8: Management of Rash Events by Severity Grade**

	Definition	Study Drug Action	Activities by Daya	Referral to Dermatologist and Dermatology Activities
Grade 1 rash (with or without pruritus)b	Erythema	Study drug intake may be continued at the investigator's discretion	
Day 0: optional on site visit for initial rash evaluation may be performed at the investigator's discretion.
 
Safety laboratory assessments may be performed at the investigator's discretion (recommended if visit occurs).
 
Digital pictures* of skin lesions may be taken at the investigator's discretion.
 
Determine if subject was adhering to the recommended sun-protective measures. If appropriate, provide sun protection counseling.
 
Day 1 and thereafter: appropriate follow-up visits at the investigator's discretion until resolution of rash.
 
Safety laboratory assessments and photography (digital pictures* of skin lesions) may be performed at the investigator's discretion.
	Not required
Grade 2 rash (with or without pruritus)b	Diffuse, maculopapular rash, or dry desquamation	Study drug intake may be continued at the investigator's discretion	
Day 0: required on-site visit (if a visit is not possible, telephone contact with the subject should take place to collect information and give advice on the necessary measures to be taken).
 
Safety laboratory assessments may be performed at the investigator's
	
Referral to dermatologist at the discretion of the investigatorc
 
Biopsy not required, but may be performed at the dermatologist's

**Table 8: Management of Rash Events by Severity Grade**

Definition	Study Drug Action	Activities by Day a	Referral to Dermatologist and Dermatology Activities
		
discretion (recommended).
 
Digital pictures* of skin lesions may be taken at the investigator's discretion.
 
Digital pictures* of skin lesions are recommended in case consultation of a dermatologist is required. Determine if subject was adhering to the recommended sun-protective measures.
 
If appropriate, provide sun protection counseling.
 
Day 1 and thereafter: appropriate follow-up visits at the investigator's discretion until resolution of rash or until clinical stability is reached.
 
Safety laboratory assessments are required on Day 1 and are required thereafter only if the previous values were abnormal (but may be performed at the investigator's discretion). If the rash progresses to a higher grade, safety laboratory assessments of the higher grade should be followed.
 
Digital pictures* of skin lesions may be taken at the investigator's discretion.
	discretion

\* Digital pictures to be taken at the clinical site.

**Table 8: Management of Rash Events by Severity Grade**

	Definition	Study Drug Action	Activities by Daya	Referral to Dermatologist and Dermatology Activities
Grade 3 rashb	
Vesiculation, moist desquamation, or ulceration OR
 
Any cutaneous event with 1 of the following:
 
 
- Elevations in AST/ALT <math>>2\times</math>baseline value
 
- Fever <math>>38^{\circ}\text{C}</math> or <math>100^{\circ}\text{F}</math>
 
- Eosinophils <math>>1.00\times 10^3/\mu\text{L}</math>
 
- Serum sickness-like reaction
 
	
Must permanently discontinue JNJ-56136379; no rechallenge allowed
 
NA treatment may be discontinued based on investigator judgement in consultation with the sponsor
	
Day 0: required on-site visit. Safety laboratory assessments required to be performed. Digital pictures* of skin lesions may be taken at the investigator's discretion (recommended). Determine if subject was adhering to the recommended sun-protective measures. If appropriate, provide sun protection counseling.
 
Day 1: required on-site visit. Safety laboratory assessments required to be performed. Digital pictures* of skin lesions may be taken at the investigator's discretion (recommended).
 
Further visit(s): appropriate follow-up required until resolution of rash or until clinical stability is reached.
 
Safety laboratory assessments and photography (digital pictures* of skin lesions) are recommended to be performed until the rash severity resolves to Grade 2 or Grade 1.
	
Requiredc
 
Biopsy not required, but may be performed at the dermatologist's discretion.

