## **10.2. Discontinuation of Study Treatment/Withdrawal from the Study**

### **Discontinuation of Study Treatment**

A subject will not be automatically withdrawn from the study if he or she has to discontinue study treatment before the end of the 24- or 48 week treatment phase, as applicable.

A subject's JNJ-56136379 treatment must be discontinued and NA may be discontinued based on investigator judgement in consultation with the sponsor if:

1. The subject withdraws consent.
2. The investigator believes that for safety reasons or tolerability reasons (eg, AE) it is in the best interest of the subject to discontinue study treatment.
3. The subject becomes pregnant.
4. The subject has a  $\geq$  gradea 3 rash (see [Attachment 3](#)).
5. The subject has a  $\geq$  grade 3 allergic reaction, nausea, or diarrhea.
6. The subject has a grade 4 AE or confirmed laboratory abnormality (with the exception of ALT/AST elevations) considered at least possibly related to study drugs by the investigator.
7. The subject experiences a treatment-emergent elevation of ALT  $>2x$  baseline value, in combination with either direct bilirubin  $>1.2x$  ULN or INR  $>1.5x$  ULN or serum albumin  $<$  LLN, confirmed by retesting.
8. The subject has signs of hepatic decompensation (ie, clinical evidence of ascites, bleeding varices, or hepatic encephalopathy).
9. The subject has a confirmed  $\geq$  grade 3 serum creatinine abnormality, regardless of the relationship to the study drugs. In this case, JNJ-56136379 must be discontinued. The subject may continue ETV or switch from TDF to ETV at the investigator's discretion and enter follow-up.

Subjects who are receiving TDF and develop confirmed treatment-emergent  $\geq$  grade 3 abnormalities in urinalysis, considered at least possibly related to TDF, may switch to ETV and continue JNJ-56136379 for 4-8 weeks. If the urinalysis abnormality persists at the end of the 4-8 weeks NA switching phase, JNJ-56136379 must be discontinued. Subjects may continue NA treatment at the investigator's discretion and enter follow-up.

---

a Grades in this list are per the DAIDS Toxicity Grading Scale.

If the confirmed  $\geq$  grade 3 urinalysis abnormality is not considered at least possibly related to TDF or ETV, or any other concomitant disease and its medication, JNJ-56136379 must be discontinued. Subjects may continue NA treatment at the investigator's discretion and enter follow-up.

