### **Grade 3 or Grade 4 Rash**

A grade 3 rash is defined as:

- 1. **vesiculation, moist desquamation, or ulceration OR**
- 2. **cutaneous event with one of the following (revised by the sponsor):**
  - elevations in AST/ALT more than 2 x baseline value and and  $\geq 5$  x ULN;**
  - fever  $> 38^{\circ}\text{C}$  or  $100^{\circ}\text{F}$ ;**
  - eosinophils  $> 1000/\text{mm}^3$ ;**
  - serum sickness-like reaction.**

A grade 4 rash is defined as:

- 3. **exfoliative dermatitis OR**
- 4. **a generalized rash with mucous membrane involvement, OR**
- 5. **erythema multiforme OR**
- 6. **Stevens-Johnson Syndrome, OR**
- 7. **rash associated with necrosis requiring surgery**
  - r) Subjects will **permanently discontinue** the intake of all study drug(s) and be withdrawn from the study. No rechallenge is allowed.
  - s) An unscheduled visit for initial rash evaluation (Day 0) is required.

---

- t) Assessment of safety blood samples by the local laboratory is required on the day of initial rash evaluation and the day thereafter (Days 0 and 1), and as indicated below. A copy of the local laboratory report should be de-identified and will be collected by the monitor.
- u) Digital pictures should be taken within 24 hours after the onset of the rash and on Day 1, and as indicated below.
- v) Referral to a dermatologist is required, preferably within 24 hours after the onset of the rash. A copy of the dermatologist's report should be de-identified and will be collected by the monitor.
- w) A biopsy should be performed within 24 hours after the onset of the rash. A copy of the biopsy report should be de-identified and will be collected by the monitor.
- x) Appropriate management should be undertaken and subjects should be followed until resolution of the rash.
- y) The description of the rash should be reported per 'Unscheduled Visit in Case of Rash' in the eCRF (ie, the initial rash assessment pages). The follow-up rash assessment pages of the eCRF should be completed for all follow-up visits.

For close follow-up of the rash, unscheduled visits will be performed as follows:

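### The fever limit that makes a rash Grade 3 pairs 38°C with 100°F, which are not equal, so a mandatory permanent stop of JNJ-56136379 is ambiguous for readings just below and at 38.0°C (minor)

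*Protocol*

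**What the plan says.** Table 8 in Protocol Attachment 3 sets the action for each rash grade. For Grades 1 and 2: "Study drug intake may be continued at the investigator's discretion". For Grade 3: "Must permanently discontinue JNJ-56136379; no rechallenge allowed". Grade 3 also brings required on-site visits with safety laboratory tests on Day 0 and Day 1, and a required dermatology referral.

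A rash can reach Grade 3 by its appearance or by an accompanying feature. The second route reads "Any cutaneous event with 1 of the following", and one of the features listed is "Fever >38^{\circ}\text{C} or 100^{\circ}\text{F".

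Section 10.2 of the protocol makes the consequence binding. Its list of stopping criteria opens with "JNJ-56136379 treatment must be discontinued and NA may be discontinued based on investigator judgement in consultation with the sponsor if", and criterion 4 is a rash of Grade 3 or higher, with a pointer to Attachment 3.

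The SAP carries the same temperature pair twice: in Appendix 9 ("fever $> 38^{\circ}\text{C}$ or $100^{\circ}\text{F") and in the Grade 3 row of the rash table in Appendix 10.

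**The concern.** A limit given in two units should describe one temperature, and this one does not. A site working in Celsius and a site working in Fahrenheit can give the same subject different grades.

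This is an action threshold. Crossing it ends JNJ-56136379 for that subject for good; staying below it leaves the decision with the investigator. Because 100°F is the lower and more cautious figure, the likely cost is a permanent stop that a 38°C limit would not have required, rather than added exposure. The assigned grade also feeds outputs in SAP Section 6.1: treatment-emergent events of at least Grade 3, events leading to discontinuation, and the listing of rash by grade.

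**Working it through.** **Inputs.** The two temperatures in the Grade 3 row of Table 8: 38°C and 100°F. The greater-than sign is taken to apply to both.

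**Formulas.** F = C × 9/5 + 32; C = (F − 32) × 5/9.

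**Does the pair agree?**

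- 38 × 9/5 + 32 = 100.4°F, not 100°F.
- (100 − 32) × 5/9 = 37.78°C, not 38°C.
- Gap: 38.00 − 37.78 = 0.22°C, or 100.4 − 100 = 0.4°F.

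The pair agrees only if 100.4°F is rounded to a whole degree, and neither document says that it was.

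**Which readings are split?** On a thermometer reading to 0.1°C:

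| Reading | In °F | Above 38°C? | Above 100°F? |
|---|---|---|---|
| 37.7°C | 99.86 | no | no |
| 37.8°C | 100.04 | no | yes |
| 37.9°C | 100.22 | no | yes |
| 38.0°C | 100.40 | no | yes |
| 38.1°C | 100.58 | yes | yes |

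On a thermometer reading to 0.1°F the split readings are 100.1, 100.2, 100.3 and 100.4°F (37.83, 37.89, 37.94 and 38.00°C). That is three readings on the Celsius scale and four on the Fahrenheit scale.

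**Does anything else settle it?**

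- Attachment 3 says "Grading of rash events will be based on the DAIDS Toxicity Grading Scale", but the scale's temperature limits are not reproduced in either document. SAP Appendix 9 says the sponsor adapted the DAIDS rash grades and marks the cutaneous-event criterion as sponsor-revised, so the scale might not decide the point in any case.
- The protocol's physical-examination text calls for body temperature without naming a unit.
- Section 10.2 asks for abnormal safety parameters to be retested within 72 hours. A repeat reading inside the band would be just as ambiguous.

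**The case against.** The strongest reply is that the rule can be applied as it stands. The line uses the word or, so read literally either figure suffices and anything above 100°F is Grade 3. Read instead as a unit pair, each site still has a usable number. The Fahrenheit value looks like whole-degree rounding, and Celsius comes first and carries the sign, which suggests that 38°C is the main figure.

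Several provisions also soften a borderline case. Below Grade 3, continuation is discretionary rather than automatic. Section 10.2 criterion 2 already requires a stop when the investigator judges it best for the subject. SAP Appendix 9 says every rash will be discussed with the sponsor. SAP Section 6.4 pools forehead, oral and tympanic temperatures as one parameter, so the documents do not standardise temperature closely enough for a 0.22°C band to stand out.

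Much of this stands as an argument about weight. It does not remove the mismatch. The two workable readings give different limits, and a reader cannot tell from the text which applies. Rounding may explain where 100°F came from, but it does not tell a site what to do at 37.9°C. It is also fair that nobody can say from the documents which limit was intended, so a stop at 37.9°C cannot simply be called a mistake.

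**Conclusion.** The line is wrong as written, and the error is minor. One mandatory stopping rule gives two answers for temperatures above 37.78°C up to and including 38.0°C.

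This rests on applying the greater-than sign to both figures. If 100°F exactly was also meant to qualify, the band gains the single reading of 100.0°F. The rule bites only when the rash is otherwise Grade 1 or 2 and no other Grade 3 feature is present. The number of subjects affected cannot be estimated, because the documents give no rash or fever incidence. The primary endpoint, sample size and error rates are unaffected. It deserves correction because it governs an irreversible treatment decision and costs almost nothing to put right.

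**What to change.** Replace the pair in Table 8 with one limit and its true equivalent:

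- if 38°C is intended: above 38.0°C (above 100.4°F);
- if 100°F is intended: 37.8°C or higher (above 100.0°F). The Celsius side should include 37.8°C, because 37.8 × 9/5 + 32 = 100.04°F is already above 100°F.

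The choice belongs to the sponsor's clinicians. Put the same line in SAP Appendices 9 and 10. The cost is one line in three places, with no new data and no new procedure.

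This corrects the temperature pair only. SAP Appendix 9 departs from Table 8 in larger ways: it requires a permanent stop at Grade 2 and adds a 5 × ULN condition to the AST/ALT feature. Those differences would remain and need separate attention.
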